### 11.5 RECORDING OF AEs

All adverse events identified between consent and 7 days after randomisation for each participant will be recorded in the medical notes for each participant. Only those events which would meet the criteria of seriousness and also qualify for reporting to the sponsor (see section 11.6.2) will be recorded on AE logs/ SAE forms and will be assigned the appropriate MedDRA Systems Organ Class (SOC) code.

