### **11.6.2 Reporting of SAEs/SARs/SUSARs and exemptions**

All SAEs that meet the definition given in section 11.1 and occur between consent and 7 days afterwards should be reported to the Sponsor unless they meet the exemption criteria below. These are outcome events are anticipated to occur in this participant group and will be exempt from reporting to the Sponsor:

Death related to infection (including multi-organ failure)

Critical care (HDU/ICU) admission

Acute kidney injury

Pulmonary oedema,

Allergy or anaphylaxis

Events That Are Common in the Trial Population:

The primary event of infection is classified as a pre-existing condition. As such, the occurrence or expected progression of infection or sepsis-related events including death will occur. In addition, participants are likely to have many minor adverse events during the course of the trial. These events will be recorded in the medical records and assessed in the same way as AE/SAEs. However, they are not usually recorded as AEs/SAEs, unless they are thought to be related to participant involvement in the trial.

Abdominal pain, nonspecific or related to a pre-existing condition

Accidents (domestic, traffic, occupational) including falls

Agitation or Anxiety

Atrial fibrillation or another cardiac dysrhythmia

Bleeding

Blood result abnormality (outside lab reported normal range) requiring no clinical intervention

Breathlessness related to a pre-existing condition e.g. COPD

Chest pain, non-specific or related to a pre-existing condition

Confusion or delirium

Constipation

Deep vein thrombosis/venous thromboembolism

Diarrhoea and/or vomiting

Dizziness or light headedness including vertigo

Dysphagia

Embolism

Fatigue, tiredness or sleepiness (somnolence)

Gastrointestinal disturbance, non-specific

Headache

Hypotension (if related to infection)

Hypoxia (if related to infection)

Incontinence, urinary or faecal

Malignancy, new diagnosis or new treatment for existing diagnosis

Mild ankle swelling not requiring treatment

Mood disorders

Muscle twitching

Any musculoskeletal condition e.g. arthritis or mechanical back pain

Peripheral vascular disease

Pneumothorax

Pressure sores or skin ulceration

Procedures occurring as part of the management of infection e.g. urinary catheter, central venous line, arterial line, intubation

Seizure

Sinus tachycardia (if related to infection)

Visual Loss e.g. cataract or macular degeneration or retinal detachment

Weight loss

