Any other known complications of, or symptoms related to infection or sepsis

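### The outcome-event exemption in Protocol 11.6.2 is not limited to events unrelated to the IMP, so a serious non-fatal reaction of an exempt type, most clearly anaphylaxis, has no stated route to ACCORD

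*Protocol*

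**What the plan says.** Section 11.6 sets the general rule: a site that learns of an SAE tells ACCORD within 24 hours, and the report carries causality and expectedness. Section 11.6.2, headed "Reporting of SAEs/SARs/SUSARs and exemptions", then makes an exception. SAEs that "occur between consent and 7 days afterwards should be reported to the Sponsor unless they meet the exemption criteria below". The exempt outcome events are infection-related death, critical care admission, acute kidney injury, pulmonary oedema, and allergy or anaphylaxis: "These are outcome events are anticipated to occur in this participant group and will be exempt from reporting to the Sponsor".

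A second list follows, of events common in this population. The paragraph introducing it speaks of progression of infection, sepsis-related events and minor events. It says these are not usually recorded as AEs or SAEs "unless they are thought to be related to participant involvement in the trial". The list ends with a catch-all: "Any other known complications of, or symptoms related to infection or sepsis".

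Section 11.5 governs the forms. "Only those events which would meet the criteria of seriousness and also qualify for reporting to the sponsor" go on AE logs or SAE forms and receive a MedDRA code; other events stay in the medical notes.

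**The concern.** Exempting anticipated outcomes from expedited reporting is a reasonable choice in a sepsis trial. The difficulty is that the exemption is defined by type of event alone, so it also removes events that the investigator attributes to the IMP. Allergy or anaphylaxis is the type for which attribution is most plausible. Section 11 states that the SPC mentions rare anaphylactic events with albumin, and 11.4.3 says that life-threatening SARs should usually be treated as unexpected. Under the protocol's own rules, a related, life-threatening, non-fatal anaphylaxis would therefore usually be a candidate SUSAR. Yet 11.6.2 releases the site from telling the sponsor about it.

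What is at stake is case-level safety reporting: the SUSAR deadlines, the content of the annual report, and the trial's tabulation of events by relatedness. The mortality and recruitment analyses are not touched.

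**Working it through.** No calculation applies. The check is to set the sections side by side and look for either a relatedness limit on the exemption or another route to ACCORD.

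**1. Is the exemption limited by relatedness?** Of the five exempt outcome events, only death carries a causal qualifier: "Death related to infection (including multi-organ failure"). The other four are listed bare. The drafters used qualifiers elsewhere in the same section: three entries of the second list (hypotension, hypoxia, sinus tachycardia) are conditioned on infection, for example "Hypotension (if related to infection").

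**2. Does the carve-out for related events reach the outcome list?** It is attached to the second list, which has 34 entries plus the catch-all, 35 in all.
- Allergy or anaphylaxis: not named in the list, and a reaction to the fluid is neither progression of infection, nor a complication of sepsis, nor a minor event. The carve-out does not reach it.
- Acute kidney injury, pulmonary oedema, critical care admission: not named, but they can be argued in as complications of sepsis or sepsis-related events. For these the text is ambiguous.

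**3. Do the general rules rescue an exempt reaction?** Section 11.3 would put any serious AE on an SAE form, and 11.6 would send it within 24 hours. But 11.6.2 is an express exception to 11.6, and 11.5 narrows the forms to events that qualify under 11.6.2. With no form, the causality and expectedness assessment does not reach ACCORD.

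**4. What depends on ACCORD being told?** Section 11.7 counts 7 days (fatal or life-threatening SUSARs) or 15 days (other SUSARs) from ACCORD's awareness. The annual report lists SARs and SUSARs that were reported.

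**5. What depends on the AE log?** SAP 4.7 tabulates events by MedDRA code, severity, relatedness, expectedness and outcome, and 11.5 assigns MedDRA codes only to events on the logs and forms. SAP 4.9 lists adverse events and SUSARs. An event kept in the medical notes and outcome fields would be absent from both.

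**6. What other capture exists?** The schedule in 7.1 records acute kidney injury, pulmonary oedema and allergy or anaphylaxis at discharge; section 1.1 gives a median stay of 10 days in this population. SAP 4.6 row 7 analyses these outcomes. Section 11 sends anaphylaxis data to the DMC, with no interval stated. None of these is a report to ACCORD.

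**Lesser point: start of the window.** Section 11.6.2 covers SAEs that occur from consent onward. Section 5.2.3 lets a participant receive allocated treatment before deferred consent is resolved, and section 3 sets the treatment phase at 6 hours from randomisation. If consent comes later than that, the whole treatment phase precedes the sponsor-reporting window. Sections 11.2 and 11.5 are worded more loosely (events recorded, reported or identified from consent), and 7.1 marks adverse events at Day 0, so the gap lies mainly in sponsor reporting.

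**The case against.** The best case for the plan is that related events are covered elsewhere. Section 9 says adverse event data, outcomes included, will be collected and reported as the authorities require; 13.2 commits the trial to the clinical trials regulations; 11.4 requires causality for every AE; and the DMC sees anaphylaxis data unblinded. This is real mitigation: the events are not lost to the trial. But the section 9 sentence sits in the paragraph on withdrawn or absent consent, and neither it nor 13.2 gives a form, deadline or recipient. A site following 11.5 and 11.6.2 literally would not send the case.

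The SUSAR exposure is also uncertain. Section 11.1 defines a SUSAR by reference to the SPC, which is not supplied, and section 11 indicates that anaphylactic events are already mentioned there. Many reactions may then be expected SARs. The wording of 11.4.3 points to life-threatening cases but does not settle each one.

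A reader might infer several stronger things that the documents do not support:
- *All related serious reactions lack a route.* They do not. Types on neither list are reportable under 11.6.2, and those on the common-events list have the carve-out. The death exemption covers only infection-related death, so a fatal reaction not related to infection is not exempt.
- *Every exempt type without a qualifier is equally affected.* Only allergy or anaphylaxis is free of a contested reading. A count of unqualified types is not a measure of impact.
- *Sections 11.6 and 11.6.2 contradict each other.* The second is an express exception to the first.
- *These reactions will be missing from the annual report.* The investigator prepares that report and the trial holds the outcome data, so omission is a risk and not a stated result.

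**Conclusion.** The point holds for serious, non-fatal events of an exempt type that are assessed as Possibly Related to the IMP. It is clear for allergy or anaphylaxis and arguable for pulmonary oedema, acute kidney injury and critical care admission. For these the protocol states no route to ACCORD, and the SAP safety tables and listings would not show them. It should be fixed.

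The number of cases cannot be estimated: the documents call anaphylactic events rare and give no rate for the other types. The conclusion assumes that sites follow 11.5 and 11.6.2 as written and that SAP 4.7 and 4.9 draw on the AE logs and SAE forms. The consent-window gap is secondary; the share of participants entered by deferred consent is not given.

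**What to change.** In 11.6.2, state that the outcome-event exemption applies only to events assessed as Unrelated to the IMP under 11.4.2, and that serious events of these types assessed as Possibly Related follow the 24-hour route in 11.6. Section 11.5 then follows through its cross-reference, and the SAP needs no change.

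Section 11.4.2 assesses relation to the IMP, which the trial summary gives as 5% HAS only; balanced crystalloid is the comparator. For the IMP no new assessment is needed, because 11.4 already requires causality for each AE. If reactions to the comparator are also to be covered, 11.4.2 must be extended to say so, and that would be an added assessment.

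For the lesser point, start the AE/SAE window at the earlier of consent or randomisation in 11.6.2, and match the start in 11.2 and 11.5.

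The cost is one protocol amendment and some additional SAE forms, probably mostly for acute kidney injury or pulmonary oedema, since 11.4.2 offers only two causality categories. Their number cannot be estimated from the documents. The SAP abstract describes recruitment in the past tense; if recruitment has closed, the sponsor can instead review the recorded allergy, pulmonary oedema and acute kidney injury outcomes for serious related events that were never reported.

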#### **5.5.3 Emergency Unblinding Procedures**

The study will be not be blinded, treating clinicians will be aware of which treatment the participant is receiving.

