### 11.2 IDENTIFYING AEs AND SAEs

Participants will be asked about the occurrence of AEs/SAEs during the study and the medical records will be reviewed to identify these. AEs and SAEs will only be recorded and reported from consent until 7 days after randomisation due to the well-known safety profiles of the interventions. Open-ended and non-leading verbal questioning of

the participant will be used to enquire about AE/SAE occurrence. Participants will also be asked if they have been admitted to hospital, had any accidents, used any new medicines or changed concomitant medication regimens. If there is any doubt as to whether a clinical observation is an AE, the event will be recorded.

AEs and SAEs may also be identified via information from support departments e.g. laboratories.

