#### **11.3.2 Worsening of the Underlying Condition during the Trial**

Medical occurrences or symptoms of deterioration that are expected due to the participant's underlying condition should be recorded in the patient's medical notes and only be recorded as AEs on the AE log if medically judged to have unexpectedly worsened during the study. Events that are consistent with the expected progression of the underlying disease should not be recorded as AEs.

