## 4.7 Safety

Summary tables of adverse events, by treatment group and overall. Number of events and number of patients who had an event, showing all adverse events, serious adverse events, and non-serious adverse events. Tables will also be presented, stratifying events by MedDRA code; severity; relatedness; expectedness; and outcome.

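### For serious events on the Protocol 11.6.2 list or under its sepsis catch-all, entry to the AE record usually turns on an unblinded relatedness judgement, so the SAP 4.7 counts do not validly compare the arms for those events

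*Protocol*

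**What the plan says.** **What reaches the record.** Protocol 11.5 sends all adverse events up to 7 days after randomisation to the medical notes. The AE logs and SAE forms receive "Only those events which would meet the criteria of seriousness and also qualify for reporting to the sponsor", with a reference to 11.6.2.

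**The filter in 11.6.2.** There are two groups.
- Anticipated outcome events (infection-related death, critical care admission, acute kidney injury, pulmonary oedema, allergy or anaphylaxis) "will be exempt from reporting to the Sponsor". No relatedness clause is attached to this exemption.
- Common events stay in the medical records, and "they are not usually recorded as AEs/SAEs, unless they are thought to be related to participant involvement in the trial". This list includes dysrhythmia, bleeding, venous thromboembolism, embolism, pneumothorax and seizure, and ends with "Any other known complications of, or symptoms related to infection or sepsis".

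**Other recording instructions.** Section 11.3.2 says that expected deterioration should "only be recorded as AEs on the AE log if medically judged to have unexpectedly worsened during the study". Section 11.2 says: "If there is any doubt as to whether a clinical observation is an AE, the event will be recorded".

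**Who judges.** Section 5.5.3 states that "treating clinicians will be aware of which treatment the participant is receiving". Section 11.4.2 has the Investigator assess causality against the IMP, and the trial summary names only 5% HAS as IMP.

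**The analysis.** SAP 4.7 plans "Summary tables of adverse events, by treatment group and overall": numbers of events and of patients with an event, for all, serious and non-serious events, with further tables by MedDRA code, severity, relatedness, expectedness and outcome. It does not mention the filter.

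**The concern.** A by-arm adverse event table is normally read as a comparison of how often events happened. For the listed and sepsis-related events, an opinion about cause usually comes before recording, and it is formed by someone who knows which fluid was given. If that opinion is formed differently in the two arms, the counts differ even when true frequencies are equal, and a real difference can be hidden.

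This concerns which events enter the table at all. It is separate from how recorded events are then classed for relatedness.

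The trial is meant to inform a definitive trial. An attribution artefact read as a safety signal for one fluid, or a real signal missed in the other, could carry over into that design. The exposed events are those with no endpoint of their own: dysrhythmia, bleeding, thromboembolism and seizure are the clearest examples.

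**Working it through.** The plan states no figure on this point, so there is none to reproduce. The check is a reading of the provisions, followed by arithmetic for scale.

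**Step 1: route onto the AE log, by type of serious event.**

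| Type of serious event | Usual condition for the AE log | Counted by arm elsewhere |
|---|---|---|
| Not listed, not exempt, not infection-related | Serious (11.5, 11.6.2) | Not needed |
| Exempt outcome event | Exempt from sponsor reporting | SAP 4.4 and 4.6: mortality, critical care admission, AKI, pulmonary oedema, allergy |
| Listed or under the sepsis catch-all | Serious and thought related to the trial (11.6.2), or unexpected worsening (11.3.2) | Partly: vasopressors, renal replacement and ventilation in SAP 4.6; none for dysrhythmia, bleeding, thromboembolism or seizure |

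The third row is the problem. Both of its routes are judgements made with the arm known. Section 11.4 asks for events to be assessed as though on active IMP only in double-blind studies, so it gives no protection here.

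**Step 2: what the table estimates.** Let r be the 7-day risk of a serious listed or sepsis-related event, q the probability that such an event reaches the log, and n the number per arm (subscript 1 for HAS, 0 for crystalloid).

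- Expected patients in the table per arm = n × r × q
- Ratio shown = (r1 / r0) × (q1 / q0)

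The SAP 4.7 table cannot tell the two factors apart. For example, a true ratio of 0.5 with a recording ratio of 2 shows as 0.5 × 2 = 1.

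**Step 3: does the relatedness split repair this?** Only in part. Listed events judged unrelated are mostly absent in both arms, so the related stratum has no complement. The headline all-event and serious-event counts still add gated to ungated events.

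**Step 4: scale.** Inputs from the documents: 300 participants (Protocol 4.1) and 1:1 allocation (5.5.1), so n = 150. Assumptions, since the documents give no rates: equal true risk r of 2% to 5%, and the recorded shares shown.

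| Recorded share, HAS vs crystalloid | r = 2% | r = 5% | Ratio shown |
|---|---|---|---|
| 5% vs 2% | 150 × 0.02 × 0.05 = 0.15 vs 150 × 0.02 × 0.02 = 0.06 | 0.375 vs 0.15 | 2.5 |
| 10% vs 2% | 0.30 vs 0.06 | 0.75 vs 0.15 | 5 |
| 20% vs 5% | 0.60 vs 0.15 | 1.50 vs 0.375 | 4 |

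Swapping the shares inverts the ratios to 0.4, 0.2 and 0.25. The ratio can be far from 1 when true risks are equal, but it then rests on about one patient per arm or fewer.

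**Step 5: consistency of the recording rules.** Section 11.2 says to record in case of doubt, 11.3.2 uses unexpected worsening, 11.5 requires seriousness and reportability, and 11.6.2 uses relatedness to the trial. SAP 4.7 asks for rows of all and of non-serious events, yet 11.5 keeps non-serious events off the log. Those rows would be empty or unevenly filled.

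**The case against.** **The gate is not absolute.** Section 11.6.2 says such events are not usually recorded, which is weaker than never; 11.3.2 offers a second route, and 11.2 favours recording when in doubt. This stands, and the point is worded accordingly. The second route is still an unblinded judgement. The 11.2 instruction concerns whether an observation is an AE, and 11.5 sends every AE to the notes but only a subset to the log.

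**Most listed events are minor.** This stands. A reader might assume that 20% to 40% of patients have a listed event and infer, at 10% versus 2% recorded, 3 to 6 versus 0.6 to 1.2 patients. That base rate counts events such as constipation and headache, which 11.5 keeps off the log in either arm unless serious.

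**The direction is not known.** A reader might infer that events after HAS will be attributed more readily, because HAS is the named IMP and crystalloid is routine care. The documents do not establish this. The filter refers to involvement in the trial, which covers both arms, and 11.2 relies on well-known safety profiles for both fluids.

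**Important harms are counted without attribution.** This stands. SAP 4.4 and 4.6 cover mortality, critical care admission, vasopressors, renal replacement, ventilation, AKI, pulmonary oedema and allergy. Vital signs to 7 hours and any routine bloods to day 7 are also collected.

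**The analysis is informal.** SAP 3 treats all tests as descriptive, and SAP 4.9 already lists adverse events. This lowers the stakes, but a descriptive by-arm table still invites comparison.

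**Any split needs judgement too.** This stands. The catch-all, and qualifiers that depend on a link to infection, make list membership partly a matter of opinion.

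**Conclusion.** The point holds for one class of events: serious events on the 11.6.2 list or under its sepsis catch-all, above all those with no endpoint of their own. For these, the SAP 4.7 by-arm counts mix true frequency with unblinded attribution and are not a valid between-arm comparison. That conclusion rests on the text of 11.5, 11.6.2, 5.5.3 and SAP 4.7, and needs no assumed rates.

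Direction and size are unknown. Under the assumptions in the working, the ratio shown ranges from 2.5 to 5 (or 0.2 to 0.4 if the shares are swapped) with equal true risk, on expected counts of 0.06 to 1.5 patients per arm.

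A reader might go further and infer that the whole SAP 4.7 table reflects attribution more than harm. The documents do not support that: serious events outside the list and unrelated to infection are reportable whatever their cause, and no attribution rates are given. Nor is the trial's comparative safety information lost, because the SAP 4.6 outcomes are not gated in this way.

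**What to change.** In SAP 4.7:

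1. Flag each recorded event by whether its type falls under the 11.6.2 list or the sepsis catch-all, with the flag assigned blind to arm.
2. Base the between-arm description of harm on the SAP 4.6 outcomes (mortality, critical care admission and interventions, AKI, pulmonary oedema, allergy) and on unlisted serious events. Describe the latter as less selected, not as free of attribution.
3. Give the listed and sepsis-related events as a case listing, without comparing counts between arms. The SAP 4.9 listing can largely serve.
4. State the recording filter as a caveat beside the tables.
5. Reconcile Protocol 11.2, 11.3.2, 11.5 and 11.6.2 with the SAP 4.7 rows for all and for non-serious events, and say what those rows can contain.

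No new data are needed, which matters because the SAP abstract describes the 300 participants as already recruited. The cost is a paragraph in the SAP, a short blinded classification step (System Organ Class coding alone will not identify list membership), a split table, and fewer events in the part that is compared.

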## **11.7 REGULATORY REPORTING REQUIREMENTS**

ACCORD is responsible for pharmacovigilance reporting on behalf of the co-sponsors (The University of Edinburgh and NHS Lothian).

ACCORD has a legal responsibility to notify the regulatory competent authority and relevant ethics committee (Research Ethics Committee (REC) that approved the trial). Fatal or life threatening SUSARs will be reported no later than 7 calendar days and all other SUSARs will be reported no later than 15 calendar days after ACCORD is first aware of the reaction.

ACCORD (or delegate) will inform Investigators at participating sites of all SUSARs and any other arising safety information.

ACCORD will be responsible for providing safety line listings and assistance; however, it is the responsibility of the Investigator to prepare the Development Safety Update

Report. This annual report lists all SARs and SUSARs reported during that time period. The responsibility of submitting the Development Safety Update Report to the regulatory authority and RECs, lies with ACCORD.

